## 8.5 Randomization and Volunteer Assignment

Volunteer assignment to each of the two experimental conditions is semi-randomized (i.e. random except that computer ensure equal sample sizes across experimental conditions). The randomized assigning of participants is done by the study web-page/program at volunteerscience.com. The computer program randomly assigned volunteers to one of the two conditions when they begin the study.

## 8.6 Volunteer Identification

Personally identifiable information (PII) will not be collected. The only identifiers linking an individual to the study would be their MTurk ID. However, the MTurk ID does not contain PII and is a randomly generated alpha-numeric code (e.g., A2IGSXYYGW2BHT). The platform being used to collect data (volunteerscience.com) will not transmit these MTurk ID's to either the ARL or WRAIR research staff. Volunteerscience.com staff will replace the MTurk IDs with new random identifiers containing no PII. Thus, there are two levels of anonymity protecting volunteers.

## 8.7 Study Materials and Manipulations

### 8.7.1 HBMT

This is a training developed by the PI (see Appendix E), but based on the existing fragment lexical decision task (Neely et al., 1989) and Go/No-Go task (Fillmore et al., 2006). It was used and validated in a previous recent study (WRAIR #2574). This task is completed entirely on the computer. For this task, volunteers see incomplete word fragments (one at a time) that appear at the center of the computer screen. Most of the word fragments could be completed to form either aggressive or non-aggressive words (e.g., “K I \_ \_” could be completed as either an aggressive word, “KILL”, or a non-aggressive word “KISS”, “KILT”, etc.). Some of the fragments could only be completed to form non-aggressive words (e.g., HA \_ PY), and the remaining fragments could only form aggressive words (e.g., A \_ \_ ACK). Volunteers are instructed to respond to these cues as quickly and accurately as possible by typing a complete word that can be formed from the fragment. Volunteers are randomly assigned to either a real-training or a fake-training. Those in the real-training condition are told to try and complete each fragment to form a positive/non-aggressive word and to refrain from typing altogether if the fragment could *only* be completed as a negative/aggressive word. Participants are given 12 seconds to respond to each cue. Volunteers randomly assigned to the fake training will be told to complete the fragments with the first word that comes to mind. This fake training still exposes volunteers to the training stimuli and a computer task, but does not train inhibition or selectively prime non-hostility, which are the hypothesized mechanisms of the training. We do not believe there is a meaningful risk this task could unintentionally prime increased hostility given that prior research found no evidence of this, despite prior research including experimental conditions that were designed to use this this training to increase hostility (WRAIR # 2574). Actual responses in this task are not the primary outcome being measured. Rather, the HBMT is used to prime either hostile attribution bias or a reduction in hostile attribution bias and the key outcome measures are reported HAB, anger, and aggression.

### 8.7.2 Demographic Questions

Volunteers will be asked to provide their gender (Male, Female, Prefer not to say), level of education, and age (number only).

### 8.8 Study Procedure

The procedural flow of the experiment with estimated times for each step is outlined below. The study will not proceed until/unless the volunteer clicks that they have read the ICD and agree. The times provided are only estimates of the duration we anticipate the typical volunteer will use.

Time-point One:

- a. Volunteer arrives at study webpage and reviews ICD (estimated to take approximately 1-2 minutes)
- b. Volunteer completes trait anger questionnaire (1 minute)
- c. Volunteer Completed State Emotion Questionnaire (3 minutes)
- d. Volunteer reads instructions for real/fake HBMT (1 minute)
- e. Volunteer completes real/fake HBMT (15 minutes)
- f. Volunteer completes ACS Scale (set A) (10 minutes)
- g. Volunteer completes demographic items (< 1 minute)
- h. Volunteer is thanked for participation (< 1 minute)

Time-Point Two (24-96 hours later)-volunteers will received daily reminder e-mails via anonymous mturk.com functionality during interim.

- i. Volunteer arrives at study webpage and reviews ICD (same ICD as from time 1; estimated to take approximately 1-2 minutes).
- j. Volunteer Completes ACS (set B) (10 Minutes)
- k. Volunteer Completed State Emotion Questionnaire (3 minutes)
- l. Volunteer Completes State Measure of Aggression (10 Minutes)
- m. Volunteer is thanked for participation (< 1 minute)

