Volunteer recruitment and data collection will be done online by ARL AI's and/or staff with assistance from volunteerscience.com (the online experimental platform). Volunteers will be recruited via Amazon Mechanical Turk (MTurk) to the experimental webpage and complete informed consent electronically. A description of this clinical trial will be available on <http://www.clinicaltrials.gov>. Additionally a copy of the informed consent may be posted to a public website no later than 60 days after enrollment is completed.

Time-point 1: Volunteers will be randomly assigned to complete either the real or fake HBMT. Volunteers will also complete a brief vignette reading HAB activity, a brief measure of trait (what is typical for them) aggression, and state (how they have felt recently) anger.

Time-point 2: Volunteers will be asked to return no sooner than 24 hours and no later than 96 hours from when they completed time-point 1 to complete a following up HAB assessment (second vignette interpretation task) and brief surveys asking about aggressive behaviors and state anger during the preceding 24 hour period.

Mechanism for inviting volunteers back to complete time-point 2: The two-time point nature of this study will be explained to volunteers in both the study advertisement and in the ICD.

Additionally, a feature on MTurk will allow the volunteerscience.com to send a daily e-mail to time-one volunteers inviting them back to time-point two. This can be done without MTurk revealing the e-mail addresses of the volunteers. The e-mail will remind volunteers to please return at any point between 24 hours and 96 hours from when they completed the first time-point.

Upon completion of each time-point, the webpage will thank volunteers for their participation. Volunteers will be paid part of the payment at the end of time-point one and the remaining payment after completing time-point two (see section 10.6).

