*Hostile Bias Modification Training* (HBMT) is a new computer task training for reducing HAB developed by scientists at WRAIR and ARL. The training is based on the Go/No-Go task (Fillmore et al., 2006) and Lexical Decision Task (Lepore and Brown, 2002). The training is theorized to reduce bias by affecting two key factors that drive HAB: relative cognitive accessibility of hostile concepts and rapid attribution-making/aggressive responding in response to ambiguously hostile cues. The training is designed to prime trainees to interpret ambiguous information as non-hostile (by increasing the saliency of non-hostile concepts) and to behaviorally commit to that interpretation quickly. Further, the training is designed to condition the individual to inhibit responding to hostile interpretations before reconsidering the possibility the information may be non-hostile. Relatedly, the training conditions the individual to inhibit responding (behaviorally) to hostile cues. Thus, the training is thought to induce a non-hostile attribution bias while simultaneously training the inhibition behavior in response to provoking cues. In a recent study (WRAIR #2574), online volunteers who completed one session of real HBMT displayed significantly less HAB when asked to interpret the motives of characters in hypothetical vignettes than volunteers who completed a fake version of the training. Although WRAIR #2574 demonstrated HBMT can affect HAB and anticipated behaviors in hypothetical situations, it did not assess real behaviors. Therefore, it is still unclear if and how HBMT is able to affect actual behaviors and anger in real life. The present study would answer this question.

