## 9 STATISTICAL METHODS AND DATA ANALYSIS

### 9.1 Analyses for Main Study Hypotheses

Between group differences (comparing real vs. fake HBMT) in the change in state anger and state HAB across time points (change from time-point one to time-point two) will be primarily assessed with a mixed-designs ANOVA. Between group differences in state aggression measured at time-point two will be assessed with a General Linear Models (GLM) analysis controlling for trait anger and demographics (age and gender).

We will also plot effect of group comparing real vs. fake HBMT and time between time-points (24-96 hours) on change scores (time 2 anger/aggression minus time 1 anger aggression) and analyze this using a linear regression with an interaction term.

Lower order effects will be tested using corrected Fishers LSD, Tukey, Scheffe, or other pairwise test as appropriate. Appropriate data-transformations may be used as necessary to satisfy significance test requirements. Lower order effects will also be assessed with pairwise dependent means t-tests. Age and gender will be controlled as covariates. Mediation analyses (if used) will be performed using non-parametric Monte-Carlo bootstrapping procedures using PROCESS (see Hayes, 2017).

We may use age, gender, and trait measures as control variables in analyses.

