**Someone talks down/is condescending to you.**

- |  | Very
Unlikely      | Unlikely              | Somewhat
Likely    | Likely                | Very
Likely        |
|--|-----------------------|-----------------------|-----------------------|-----------------------|-----------------------|
| 43. I can't stand having to hear this.   |  |  |  |  |  |
| 44. People are so rude. / He/she always acts this way.   |  |  |  |  |  |
| 45. He/she just thinks he/she's better than me. / I know he/she is just trying to make me upset. |  |  |  |  |  |
| 46. I hate this arrogant/conceited/stuck-up loser!   |  |  |  |  |  |
| 47. I shouldn't have to listen to this. / People can't talk to me this way.                      |  |  |  |  |  |
| 48. Even though I don't like hearing this, I can't control what others say to me.                |  |  |  |  |  |

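### Every volunteer answers ACS set A at time 1 and set B at time 2, so the group-by-time HAB term cannot separate a change in the training effect from a difference between the sets in sensitivity to training

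*Combined protocol and SAP*

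**What the plan says.** In section 8.8, time-point one runs the training first (step e, "Volunteer completes real/fake HBMT (15 minutes") and then the ACS (step f, "Volunteer completes ACS Scale (set A) (10 minutes"). At time-point two, step j is "Volunteer Completes ACS (set B) (10 Minutes". Section 3.3 describes the later measure as a "following up HAB assessment (second vignette interpretation task".

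Only training condition is randomised. Section 8.5 states: "The computer program randomly assigned volunteers to one of the two conditions when they begin the study". No section describes rotating the sets, equating them or using linking items.

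Appendix B shows that the sets share no scenario. Set A has four: a car backing out, a roommate's dirty kitchen, a bump at the mall and a wrong drive-thru order. Set B has five: a slow driver, clerks ignoring a customer, a partner's broken promise, condescension and an unsupportive family. Subscales are scored as raw sums.

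The planned analysis in section 9.1 is a mixed-designs ANOVA of "Between group differences (comparing real vs. fake HBMT) in the change in state anger and state HAB across time points". Section 3.4 lists HAB among the main endpoints, and section 3.1 makes shifts in HAB the secondary, mechanistic objective.

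**The concern.** Both ACS administrations follow the training, so there is no pre-training HAB score. The group-by-time term therefore does not test whether training lowers HAB. It tests whether the arm difference changes between the sessions, and that is the quantity which the fixed set order contaminates.

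Unequal sensitivity is possible on the protocol's own account. Section 6.1 says the training works partly on "rapid attribution-making/aggressive responding in response to ambiguously hostile cues". The set A scenarios mostly leave intent open, whereas at least one set B scenario states the slight outright ("Someone talks down/is condescending to you"), and the family scenario comes close to doing so. If training moves responses less on stated slights, the arm difference shrinks from set A to set B with no change over time. A significant result could then be read as a fading effect on HAB, and nothing in the planned analysis could show otherwise.

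**Working it through.** **Inputs from the documents.** 100 completers per arm, d = .78 for HAB measured immediately in the earlier study, and d = .40 for planning (all section 7.2); α = 0.05 (section 9.2).

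**Assumptions not in the documents.** Item-mean scores with SD 1 on each set; r = .4 to .7; and k, the training effect on set B as a fraction of that on set A. With no effect on two of the five set B scenarios, k = 3/5 = 0.6. With half the effect on those two, k = (3 + 2 × 0.5)/5 = 0.8. With three quarters, k = (3 + 2 × 0.75)/5 = 0.9.

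**The plan's own figure.** n per arm = 2(1.96 + 0.842)²/0.4² ≈ 98.1, so 99 per arm and 198 in all, against the stated 200. This reproduces with a two-sided test. It sizes a comparison of two means, not a group-by-time contrast.

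**What the term estimates.** Let the training effect be d₁ at time 1 and d₂ at time 2, in set A units. The arm difference is d₁ on set A and k·d₂ on set B. The group-by-time contrast is d₁ − k·d₂ = (d₁ − d₂) + (1 − k)·d₂. The first part is true fading and the second is set sensitivity; one observed contrast cannot yield both. With no fading, the contrast is (1 − k)·d.

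**Mean level alone.** If set B simply scores higher or lower in both arms, the shift cancels. With a 0.5 SD shift, k = 1 and r = .5, simulation gave a contrast of 0.000 and rejection of 0.051.

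**False rejection.** SE = √(2(1 − r)) × √(2/100), which is 0.155, 0.126 and 0.110 at r = .4, .6 and .7. Rejection is from the two-sided noncentral t on 198 df. For example, at d = .78, k = 0.6 and r = .4, 0.312/0.155 = 2.01, which gives 52%.

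| d | k | False contrast (1 − k)d | Rejection at r = .4 / .6 / .7 |
|---|---|---|---|
| .78 | 0.6 | 0.312 | 52% / 69% / 81% |
| .78 | 0.8 | 0.156 | 17% / 23% / 29% |
| .78 | 0.9 | 0.078 | 8% / 9% / 11% |
| .40 | 0.6 | 0.160 | 18% / 24% / 31% |
| .40 | 0.8 | 0.080 | 8% / 10% / 11% |
| .40 | 0.9 | 0.040 | about 6% throughout |

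**Scoring.** By the Appendix B table, every subscale has four items in set A and five in set B. Raw sums add a separate distortion: with k = 1 and no fading at d = .78, the contrast is 4 × .78 − 5 × .78 = −0.78 points. Item means remove this but leave (1 − k)·d untouched.

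**Counterbalanced order.** With no fading, the contrast is (1 − k)d in the A-then-B half and −(1 − k)d in the B-then-A half, so their equal-weight average is 0. Simulated rejection at r = .5 and d = .78 was 0.050 for k = 0.5 and 0.054 for k = 0.75. In a separate simulation at k = 0.6 it was 0.044–0.052, with SEs of 0.155/0.127/0.109 against 0.155/0.127/0.110 for the fixed order at r = .4/.6/.7.

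**The case against.** The strongest reply is that the protocol never asks whether the HAB effect fades. The longevity objective (4.1 b), the decay hypothesis (5.2 a) and the regression on hours between sessions (9.1) all concern anger and aggression. The Précis predicts less hostile bias at the second time-point, and Hypothesis 2 rests on between-group differences in HAB. Both are comparisons at a single time, where both arms answer the same set. All of this stands. A reader might infer that the fixed order invalidates the HAB comparison, the mediation analysis or the decay objective; the documents do not support that. What remains exposed is the HAB change test that 9.1 specifies, and any statement about shifts in HAB drawn from it.

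The second reply is that unequal sensitivity is not shown. Section 6.1 also says the training conditions people to inhibit responses to hostile cues, and Appendix E includes stems with only negative solutions, so no effect at all on stated slights sits uneasily with the protocol's theory. The sorting of scenarios is a judgement: set A's mall scenario includes the failure to apologise, and set B's slow driver leaves intent open. Each scenario carries one item per subscale, so the sets match in structure. This also stands. It is why k = 0.6 should be read as one end of a range, and it does not make k equal to 1.

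A reader might also infer that the plan will hide real fading. The algebra allows this if k exceeds 1, but nothing in the scenario content suggests that set B is the more sensitive set.

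**Conclusion.** The point holds in a limited form. The aliasing of group-by-time with group-by-set is certain from 8.5, 8.8 and 9.1, and no planned analysis removes it. Its size is not known. Across k = 0.6 to 0.9 and r = .4 to .7, the false-positive rate for HAB change runs from barely above nominal (about 6%, at d = .40 and k = 0.9) to 81% (at d = .78 and k = 0.6). The upper figures also assume that .78 persists undiminished to 24–96 hours, whereas section 7.2 expects smaller effects with delay. No single value in the table should be quoted as the expected error.

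The change is still worth making, because 9.1 makes HAB change a primary assessment, HAB is a main endpoint, and the remedy is cheap.

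**What to change.** **Preferred.** In 8.8 steps f and j, have the study program randomise set order 1:1 within each arm (A then B, or B then A), and record this in 8.5. Score the ACS by item mean. In 9.1, add set order and group-by-order to the HAB mixed model, with order centred so that group-by-time is averaged over both orders. Include set order as a covariate in any time-point-specific or mediation model that uses HAB.

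**Cost.** One more program-generated flag and one extra factor with its interaction; no added items, time or volunteers, and essentially no loss of precision on group-by-time in the simulations. The small downside is that HAB at each time is no longer on one common set. The time-2 comparison and the mediator then mix two sets, so order has to be in those models.

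**If the order cannot be changed.** State in 9.1 that HAB is compared between arms at each time point, with time 2 as the HAB test, and that no fading or persistence is inferred from the set A to set B change. This costs only that sentence and the change claim.

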### 8.9 Documents and Electronic Data Management

#### 8.9.1 Pre-Consent Documents/Recruitment Material (Appendix A)

#### 8.9.2 Consenting/Screening Documents

**8.9.2.1 ICD** (Appendix C) — provides potential volunteers' information pertaining to study procedures, risks, and benefits, and is used to document consent to participate in the study. This is displayed electronically on the study webpage at the start of the study.

#### 8.9.3 Study Documents and Materials

**8.9.3.1 UAP reporting form** (Appendix I) – Documents unanticipated problems involving risks to volunteers or others

### 8.9.3.2 Angry Cognition Scale (Appendix B)

### 8.9.3.3 Demographics Questions (Appendix D)

### 8.9.3.4 HBMT (real/fake) Stimuli and Instructions (Appendix E)

### 8.9.3.5 State Aggression Questionnaire (Appendix F)

### 8.9.3.6 Trait anger Questionnaire (Appendix G)

### 8.9.3.7 State emotion Questionnaire (Appendix H)

## 8.10 Unanticipated Problems

### 8.10.1 Definition of Unanticipated Problem (UAP)

As per SOP no: UWI-B-004, unanticipated problems include any unforeseen or unexpected incident or experience (including an unanticipated adverse event) that occurs during the conduct of the research and that was not described in the information reviewed by the IRB (i.e. research protocol or informed consent document). Unanticipated problems can include subject complaints or protocol violations.

### 8.10.2 Definition of Unanticipated Problem Involving Risks to Volunteers or Others (UPIRTSO)

As per SOP no: UWI-B-004, UPIRTSO include any incident, experience or outcome that meets **all** of the following criteria:

1. Unexpected (meaning that there is a reasonable possibility that the incident, experience or outcome may have been caused by the procedures involved in the research) given (a) the research procedures that are described in the protocol-related documents, such as the IRB-approved research protocol and informed consent document; and (b) the characteristics of the subject population being studied;
2. Related or possibly related to participation in the research (in this guidance document, *possibly related* means there is a reasonable possibility that the incident, experience, or outcome may have been caused by the procedures involved in the research); and
3. Suggests that the research places subjects or others at a greater risk of harm (including physical, psychological, economic, or social harm) than was previously known or recognized.

### 8.10.3 Reporting of UAPs and UPIRTSOs

1. UAPs & UPIRTSOs will be reported to HSPB, as applicable.
2. All UPIRTSOs will be reported promptly to HSPB upon their identification (within 48 hours), and a report will be provided to HSPB within 10 working days.

## **8.11 Data Disposition**

Volunteerscience.com uses servers located in the geographic US that are owned and operated by Amazon Web Services (AWS). Volunteerscience.com will also assist with the technical aspects of collecting the data and recruiting participants (e.g., posting the advertisement to MTurk; managing the webpage). During the course of the study, data will be stored on secure servers with Federal Risk and Authorization Management Program (FedRAMP) and Defense Information Systems Agency (DISA) authorizations at the moderate impact level or higher (all US-based AWS servers meet these criteria). Data from participants are always uploaded from participant's computer to the volunteerscience.com server using secure, encrypted SSL connections. Login to access the data on the server will be retained by only the PI/AI's and authorized research staff. Passwords are always sent to the server over secure, encrypted SSL connections. See Section 11.2 for details on Information Assurance and Operational Security. Upon the completion of data collection, all data will be downloaded via .csv files (or equivalent) and deleted from AWS servers. All electronic data and files will be encrypted and kept in a password-protected folder on the MPB network drives (CMPN, WRAIR) with access restricted to study staff members on CAC-protected computers at WRAIR. Duplicates of data will also be stored on secure drives at ARL. All records (paper and electronic) will be retained for at least three years following completion of the research (submission of the study closeout report). No personally identifying information will be collected as part of this research. The only identifiers are the public MTURK user-names, which are random alpha-numeric monikers that do not contain PII. Further, even these MTURK user-names will not be retained. Volunteerscience.com replaces the MTurk usernames with new random alpha-numeric codes prior to providing data to AIs. We do not believe there is a chance these data could be re-identified later. There are no current plans to share data with any third parties; any future sharing of data will be addressed under an amendment to the protocol, with appropriate agreements in place, as applicable.

